The E-RS is a PRO instrument derived from the EXACT-PRO designed to collect data to quantify the severity of respiratory symptoms across domains of breathlessness, chest symptoms and cough/sputum in patients with COPD and evaluate treatment benefit (Exact 2013). The E-RS is an electronic instrument to be completed by the patient in the form of the EXACT-PRO in the eDiary each evening before bedtime.

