6.4. WINDOWING CONVENTIONS

Each visit (except for Day 1 visit) will have a ± 10 days window. No visit windowing will be applied during the analysis to the data that is only collected at scheduled site visits for patients that have completed the study, and therefore the data will be presented as per the visit reported in the database.

For endpoints based on 12 hour spirometry data, (FEV1 AUC0-12h, FEV1 evening trough and FEV1AUC6-12h), data collected at visits with 12 hour spirometries will be included in the analysis regardless of the timepoint it was generated. Hence, no windowing convention applied to these endpoints.

For the patients that discontinued from the study, the End of Study (EOS) visit will be windowed to the corresponding visit, based on the study day, for questionnaire, spirometry and rescue medication data. The EOS visit can only be windowed to a visit that is missing or has a missing result. The rules for the windowing are described below.

[REDACTED]	[REDACTED]	[REDACTED]	[REDACTED]
[REDACTED]	[REDACTED]	[REDACTED]	[REDACTED]
[REDACTED]	[REDACTED]	[REDACTED]	[REDACTED]
[REDACTED]	[REDACTED]	[REDACTED]	[REDACTED]

- For spirometry raw data and derived data that happens at every visit, windowing will be done as per the corresponding visits.
 - Day 1 = Day 1
 - Week 6 = after Day 1 and up to and including Day 53
 - Week 12 = after Day 53 and up to and including Day 95
 - Week 24= after Day 95 and up to and including Day 179
- For spirometry derived data that only happen at certain visits, windowing will be done for the corresponding visits.
 - For morning trough:
 - Week 6 = after Day 1 and up to and including Day 53
 - Week 12 = after Day 53 and up to and including Day 95
 - Week 24= after Day 95 and up to and including Day 179
 -
- For rescue medication data, E-RS/EXACT-PRO, e-diary data and COPD exacerbation, windowing will be done as per the corresponding visits. Specifically, rescue medication data, E-RS/EXACT-PRO, e-diary data windowing conventions will be up to Week 24 whilst COPD exacerbation will be up to Week 48.
- - For patients who completed the study or who discontinue study medication but continue in the study:
- Week 24 subset:
 - Week 1 = Actual study Day of Week 24 visit minus 168 days (inclusive) up to and including actual study day of week 24 visit minus 161 days
 - Week 2 = Actual study Day of Week 24 visit minus 161 days up to and including actual study day of week 24 visit minus 154 days

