- Week 22 = Actual study Day of Week 24 visit minus 21 days up to and including actual study day of week 24 visit minus 14 days
- Week 23 = Actual study Day of Week 24 visit minus 14 days up to and including actual study day of week 24 visit minus 7 days
- Week 24 = Actual study Day of Week 24 visit minus 7 days up to and including actual study day of week 24 visit
-
- Week 48 subset:
- Week 1 = Actual study Day of Week 48 visit minus 336 days (inclusive) up to and including actual study day of week 48 visit minus 329 days
- Week 2 = Actual study Day of Week 48 visit minus 329 days up to and including actual study day of week 48 visit minus 322 days
- Week 3 = Actual study Day of Week 48 visit minus 322 days up to and including actual study day of week 48 visit minus 315 days

[REDACTED]

- Week 4 = Actual study Day of Week 48 visit minus 315 days up to and including actual study day of week 48 visit minus 308 days
- Week 5 = Actual study Day of Week 48 visit minus 308 days up to and including actual study day of week 48 visit minus 301 days
- Week 6 = Actual study Day of Week 48 visit minus 301 days up to and including actual study day of week 48 visit minus 294 days
- Week 7 = Actual study Day of Week 48 visit minus 294 days up to and including actual study day of week 48 visit minus 287 days
- Week 8 = Actual study Day of Week 48 visit minus 287 days up to and including actual study day of week 48 visit minus 280 days
- Week 9 = Actual study Day of Week 48 visit minus 280 days up to and including actual study day of week 48 visit minus 273 days
- Week 10 = Actual study Day of Week 48 visit minus 273 days up to and including actual study day of week 48 visit minus 266 days
- Week 11 = Actual study Day of Week 48 visit minus 266 days up to and including actual study day of week 48 visit minus 259 days
- Week 12 = Actual study Day of Week 48 visit minus 259 days up to and including actual study day of week 48 visit minus 252 days
- Week 13 = Actual study Day of Week 48 visit minus 252 days up to and including actual study day of week 48 visit minus 245 days
- Week 14 = Actual study Day of Week 48 visit minus 245 days up to and including actual study day of week 48 visit minus 238 days
- Week 15 = Actual study Day of Week 48 visit minus 238 days up to and including actual study day of week 48 visit minus 231 days
- Week 16 = Actual study Day of Week 48 visit minus 231 days up to and including actual study day of week 48 visit minus 224 days

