- Week 17 = Actual study Day of Week 48 visit minus 224 days up to and including actual study day of week 48 visit minus 217 days
- Week 18 = Actual study Day of Week 48 visit minus 217 days up to and including actual study day of week 48 visit minus 210 days
- Week 19 = Actual study Day of Week 48 visit minus 210 days up to and including actual study day of week 48 visit minus 203 days
- Week 20 = Actual study Day of Week 48 visit minus 203 days up to and including actual study day of week 48 visit minus 196 days
- Week 21 = Actual study Day of Week 48 visit minus 196 days up to and including actual study day of week 48 visit minus 189 days
- Week 22 = Actual study Day of Week 48 visit minus 189 days up to and including actual study day of week 48 visit minus 182 days
- Week 23 = Actual study Day of Week 48 visit minus 182 days up to and

[REDACTED]

- including actual study day of week 48 visit minus 175 days
- Week 24 = Actual study Day of Week 48 visit minus 175 days up to and including actual study day of week 48 visit minus 168 days
- Week 25 = Actual study Day of Week 48 visit minus 168 days up to and including actual study day of week 48 visit minus 161 days
- Week 26 = Actual study Day of Week 48 visit minus 161 days up to and including actual study day of week 48 visit minus 154 days
- Week 27 = Actual study Day of Week 48 visit minus 154 days up to and including actual study day of week 48 visit minus 147 days
- Week 28 = Actual study Day of Week 48 visit minus 147 days up to and including actual study day of week 48 visit minus 140 days
- Week 29 = Actual study Day of Week 48 visit minus 140 days up to and including actual study day of week 48 visit minus 133 days
- Week 30 = Actual study Day of Week 48 visit minus 133 days up to and including actual study day of week 48 visit minus 126 days
- Week 31 = Actual study Day of Week 48 visit minus 126 days up to and including actual study day of week 48 visit minus 119 days
- Week 32 = Actual study Day of Week 48 visit minus 119 days up to and including actual study day of week 48 visit minus 112 days
- Week 33 = Actual study Day of Week 48 visit minus 112 days up to and including actual study day of week 48 visit minus 105 days
- Week 34 = Actual study Day of Week 48 visit minus 105 days up to and including actual study day of week 48 visit minus 98 days
- Week 35 = Actual study Day of Week 48 visit minus 98 days up to and including actual study day of week 48 visit minus 91 days

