 - Week 12 = after Day 78 and up to and including Day 85
 - Week 13 = after Day 85 and up to and including Day 92
 - Week 14 = after Day 92 and up to and including Day 99
 - Week 15 = after Day 99 and up to and including Day 106
 - Week 16 = after Day 106 and up to and including Day 113
 - Week 17 = after Day 113 and up to and including Day 120
 - Week 18 = after Day 120 and up to and including Day 127
 - Week 19 = after Day 127 and up to and including Day 134
 - Week 20 = after Day 134 and up to and including Day 141
 - Week 21 = after Day 141 and up to and including Day 148
 - Week 22 = after Day 148 and up to and including Day 155
 - Week 23 = after Day 155 and up to and including Day 162

[REDACTED]

- Week 24 = after Day 162 and up to and including Day 169
-
- Week 48 subset:
 - Week 1 = on or after Day 1 and up to and including Day 8
 - Week 2 = after Day 8 and up to and including Day 15
 - Week 3 = after Day 15 and up to and including Day 22
 - Week 4 = after Day 22 and up to and including Day 29
 - Week 5 = after Day 29 and up to and including Day 36
 - Week 6 = after Day 36 and up to and including Day 43
 - Week 7 = after Day 43 and up to and including Day 50
 - Week 8 = after Day 50 and up to and including Day 57
 - Week 9 = after Day 57 and up to and including Day 64
 - Week 10 = after Day 64 and up to and including Day 71
 - Week 11 = after Day 71 and up to and including Day 78
 - Week 12 = after Day 78 and up to and including Day 85
 - Week 13 = after Day 85 and up to and including Day 92
 - Week 14 = after Day 92 and up to and including Day 99
 - Week 15 = after Day 99 and up to and including Day 106
 - Week 16 = after Day 106 and up to and including Day 113
 - Week 17 = after Day 113 and up to and including Day 120
 - Week 18 = after Day 120 and up to and including Day 127
 - Week 19 = after Day 127 and up to and including Day 134
 - Week 20 = after Day 134 and up to and including Day 141
 - Week 21 = after Day 141 and up to and including Day 148
 - Week 22 = after Day 148 and up to and including Day 155
 - Week 23 = after Day 155 and up to and including Day 162
 - Week 24 = after Day 162 and up to and including Day 169
 - Week 25 = after Day 169 and up to and including Day 176
 - Week 26 = after Day 176 and up to and including Day 183
 - Week 27 = after Day 183 and up to and including Day 190
 - Week 28 = after Day 190 and up to and including Day 197
 - Week 29 = after Day 197 and up to and including Day 204

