For patients who permanently discontinue the study medication, the “Date of Visit X(n)”/ “Date of Visit Y” will be replaced by the last dose date of study medication, as specified in Section 14 of the SAP. Whereas for patients who completed study, the “Date of Visit X(n)”/ “Date of Visit Y” will be replaced by date of last dose.

Drug intake as recorded in the e-diary: percent of ‘yes’ responses. The denominator is the number of records for which the patient provided an answer (Yes or No) to drug intake questions (morning and evening) in the e-diary.

For time interval study medication e-diary compliance, use week’s windowing conventions described in Section 6.4 of the SAP. For Week 24 (for the 24-week stratum), use study day assigned to determine the date for weeks required or the time intervals, Week 12 and Week 24. The compliance will be calculated as follows:

$$\frac{(\text{Week } X^* < \text{number of 'yes' responses entered in the eDiary} \leq \text{Week } Y)}{(\text{Week } X^* < \text{number of non - missing responses entered in the e - Diary} \leq \text{Week } Y)} * 100$$

*If Week X = Day 1, update “<” to be “≤”. For the 24-week stratum, if Week Y is Week 24 and patient has completed treatment then the last entry we expect is in the morning. Patient should not log any entries from and including evening of Week 24.

Similarly for Week 48 visit for the 48-week stratum, determine the time intervals using study day as described above for Week 12, Week 24, and Week 48. As above, if Week Y is Week 48 and patient has completed treatment the last entry expected will be morning and no further log entry

[REDACTED]

should be done including the evening of Week 48.

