16.2.1.2. Questionnaires

16.2.1.2.1. E-RS™:COPD

EXACT-Respiratory Symptoms for COPD (E-RS™: COPD) data will be collected within EXACT-PRO questionnaire (consisting of 14 questions), as shown in Appendix 3. Please note that items 3, 8, 9, 10, 11 and 14 have separate scoring instructions, namely with the same raw score being assigned to several answer options. E-RS™: COPD consists of 11 questions, with subdomains of: Breathlessness, Cough and Sputum, and Chest Symptoms. This data will be collected everyday throughout the duration of the study.

Calculating the score

E-RS subdomains:

- Breathlessness – items 7, 8, 9, 10 and 11 (score range: 0-17)
- Cough and Sputum – items 2, 3 and 4 (score range: 0-11)
- Chest Symptoms – items 1, 5 and 6 (score range: 0-12)

The E-RS Total score is derived as the sum of the raw scores of the 11 items (score range: 0-40). Total and subdomain scores are derived weekly as the mean over the days within each window, as specified in the Section 6.4 of the SAP, using only days where data was recorded. Baseline is the mean over the 7 days prior to the first intake of study treatment, using only days where data was recorded. If less than 4 days of data are available for the week, the weekly mean is set to missing. Furthermore, all questions need to be answered to be evaluable for that day.

If a patient discontinued then use treatment study end date, as the date of their last expected visit.

The EXACT-PRO total score will be calculated by first summing the raw scores of all 14 items (score range: 0-51) and then looking up the corresponding EXACT-PRO total score in the table described in the Appendix 4 (converted score range: 0-100).

E-RS subdomain score is calculated as the sum from the relevant questions.

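### For 24-week-stratum treatment completers, the Week 24 diary window ends on a day with no expected evening entry, so the Week 24 E-RS mean apparently rests on at most 6 evenings, not 7

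*SAP*

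**What the plan says.** SAP 6.4 counts diary weeks back from the final visit for patients who complete the study, or who stop study medication but stay in. In the 24-week subset, "Week 24 = Actual study Day of Week 24 visit minus 7 days up to and including actual study day of week 24 visit". Only the first week has its lower bound marked as included: "Week 1 = Actual study Day of Week 24 visit minus 168 days (inclusive". For patients who leave the study, fixed days apply: "Week 24 = after Day 162 and up to and including Day 169". In the 48-week subset the window is mid-study: "Week 24 = Actual study Day of Week 48 visit minus 175 days up to and including" the Week 48 visit minus 168 days.

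Protocol 8.3.3.6 has the E-RS "completed by the patient in the form of the EXACT-PRO in the eDiary each evening before bedtime". SAP 16.2.1.2.1 takes weekly E-RS means over the 6.4 windows and adds: "If less than 4 days of data are available for the week, the weekly mean is set to missing". Its baseline is the 7 days before first dose. SAP 16.2.1.3 applies the same minimum to weekly rescue use.

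On e-diary dosing compliance, SAP 15.1.1 says of a 24-week-stratum patient who has completed treatment: "Patient should not log any entries from and including evening of Week 24". For the 48-week stratum the cut-off comes later: "if Week Y is Week 48 and patient has completed treatment the last entry expected will be morning and no further log entry". SAP 15.2 places E-RS first in the same diary sequence as study medication and judges E-RS compliance from the medication entries.

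**The concern.** The window for a confirmatory endpoint seems to include one day on which the SAP itself expects no evening entry. The 4-of-7 rule then becomes 4 of 6 for one group of patients, and some Week 24 means that would have been observed must be imputed. Week 24 E-RS stands third in the SAP 7.4 hierarchy, ahead of SGRQ total score and three further tests.

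The affected stratum is randomized 1:1 and the other 3:1, so the shortened window covers a larger share of placebo than of ensifentrine patients. Treatment duration is in neither the ANCOVA (SAP 16.1.3, 16.2.3.1) nor the imputation model (SAP 16.2.2.1).

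**Working it through.** **The plan's own figure.** The documents give no power or expected missing rate for Week 24 E-RS. The only sizing figure is for the primary endpoint (Protocol 9.2). SE = 250 × √(1/500 + 1/300) = 18.26 mL; 59/18.26 − 1.96 = 1.27; power 89.8%, which agrees with the stated 90%. Nothing below depends on it.

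**Counting days.** Let V be the study day of the Week 24 visit and V48 that of the Week 48 visit.

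- Lower bound: visit minus 7 already closes Week 23, only Week 1 is marked as inclusive, and the fixed-day rule starts after Day 162. The bound is therefore exclusive. An inclusive reading would give 8 days and 7 evenings, but would count every boundary day twice.
- 24-week completers: V−6 to V, 7 days. Without the visit-day evening, 6 evenings.
- 48-week completers: V48−174 to V48−168, 7 days. The diary continues to Week 48, so 7 evenings.
- Fixed-day rule: Days 163 to 169, 7 days.
- Week 1: V−168 to V−161, both included, 8 days. The fixed-day Week 1 (Days 1 to 8) also has 8.

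**Chance of failing the 4-day minimum.** P(X ≤ 3) with X ~ Binomial(n, p), n = 6 or 7. The daily completion probability p is an assumption. At p = 0.90:

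- n = 6: 20(0.9³)(0.1³) + 15(0.9²)(0.1⁴) + 6(0.9)(0.1⁵) + 0.1⁶ = 0.0159
- n = 7: 35(0.9³)(0.1⁴) + 21(0.9²)(0.1⁵) + 7(0.9)(0.1⁶) + 0.1⁷ = 0.0027

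The last column takes 400 completers (the whole stratum) and 300 (25% withdrawal, the Protocol 9.2 trigger).

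| Assumed p | 6 evenings | 7 evenings | Difference (points) | Extra missing means, 300–400 completers |
|---|---|---|---|---|
| 0.95 | 0.22% | 0.02% | 0.20 | under 1 |
| 0.90 | 1.6% | 0.3% | 1.3 | 4–5 |
| 0.85 | 4.7% | 1.2% | 3.5 | 11–14 |
| 0.80 | 9.9% | 3.3% | 6.6 | 20–26 |

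If missed days cluster within patients (beta-binomial, assumed correlation 0.3 to 0.5), the extra missing means are about 3–5 at 0.95, 5–10 at 0.90 and 10–20 at 0.80.

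**Split by arm.** The 24-week stratum holds 200/500 = 40% of ensifentrine and 200/300 = 67% of placebo patients. If all complete, the extra missingness at p = 0.90 is 1.31 × 0.40 = 0.52 points on ensifentrine and 1.31 × 0.667 = 0.87 on placebo, a gap of 0.35. At p = 0.80 it is 2.6 against 4.4, a gap of about 1.7.

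**Precision.** Averaging 6 rather than 7 entries multiplies the variance of the mean by [r + (1−r)/6] / [r + (1−r)/7]. This is 1.003 at an assumed within-patient correlation r = 0.9 and 1.021 at r = 0.5, so the loss is slight.

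**The case against.** The no-entry sentence is analysis text on dosing compliance, and it follows from the last dose being taken in the morning. It is not an instruction to patients about E-RS. The protocol asks for E-RS every evening with no visit-day exception, and SAP 16.2.1.2.1 describes daily collection throughout the study. The schedule row on collecting the diary cannot be read well enough to show when the device is returned. This stands: the shared diary sequence makes the inference reasonable but does not make it explicit. For rescue use the visit day is less clearly empty, because Protocol 6.7.1.1 records use at spirometry visits in the eCRF.

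The practical effect may also be small. Protocol 5.3 requires diary completion on at least 5 of the last 7 run-in days, compliance is reviewed at visits, and 4 of 6 still tolerates two missed evenings. Patients below the minimum stay in through multiple imputation that draws on all available weeks, with tipping-point, average-imputation and per-protocol analyses as support. This stands too.

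A reader might infer that the whole Week 24 E-RS endpoint rests on 6 evenings, or that the treatment comparison is biased. The documents support neither. The 48-week stratum, about 400 of 800 patients, keeps 7 evenings, and the sentence does not reach patients who stopped treatment but stayed in the study. The imbalance between arms follows from the allocation ratios alone; nothing ties the missed evenings to outcome or gives a direction.

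**Conclusion.** The window count is firm. That the visit-day evening is empty for E-RS is a sound inference, held with moderate confidence. On that basis, the key symptom endpoint is measured over one evening fewer in 24-week-stratum treatment completers than at baseline or in the other stratum, and the 4-day rule is harder to meet.

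The size depends wholly on an assumed completion rate. With independent entries it is negligible at 95%, a handful of patients at 90%, and worth notice only near 80%. This is a free improvement in how the endpoint is defined, not a threat to the validity of the E-RS test.

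**What to change.** For the weekly E-RS and rescue-use means only, amend SAP 6.4 as follows:

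- 24-week subset: Week 24 = visit day minus 7 to visit day minus 1, both inclusive. Move the earlier weeks back by one day, so that Week 1 = visit minus 168 to visit minus 162.
- 48-week subset: the same shift, so that Week 24 = Week 48 visit minus 175 to minus 169, both inclusive.
- Fixed-day rule: Week 1 = Days 1–7 and Week 24 = Days 162–168.

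Every week then has 7 evenings, and Week 24 mirrors the baseline definition. If some patients do log on the visit evening, nothing is lost: there are still 7 possible entries, all before the final morning dose.

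Leave the windows for dosing compliance and COPD exacerbations unchanged. Both need the visit day: compliance expects a morning entry then, and time in study runs to that day (SAP 16.3.3).

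The cost is SAP wording and a second window definition in the programming, settled before database lock. No new data are needed.

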7.4. MULTIPLE COMPARISONS/ MULTIPLICITY

To address multiplicity in the analysis of the endpoints, statistical testing of the primary endpoint and key secondary endpoints will be done in the hierarchical order (listed below). Initially the primary endpoint will be checked to see if comparison between active treatment and placebo is statistically significant. If yes, the first key secondary endpoint will be evaluated. If yes, the next key secondary endpoint will be evaluated. This process will continue until either all endpoints are evaluated, or if one of the endpoints' comparison is not significant.

Order of the endpoints that will be used for the hierarchical testing:

1. Change from baseline FEV₁ to FEV₁ AUC_{0-12h} at Week 12
2. Change from baseline FEV₁ to peak FEV₁ at Week 12
3. Change from baseline (i.e. mean over the last 7 days of run-in) to the mean weekly value at Week 24 in COPD symptoms, as measured by daily diary (E-RSTM:COPD)
4. Change from baseline in the SGRQ total score at Week 24
5. Change from baseline FEV₁ to morning trough FEV₁ at Week 12
6. Change from baseline FEV₁ to average FEV₁ AUC_{0-4h} at Week 12
7. Proportion of SGRQ responders at Week 24

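### In the 48-week subset, the Week 24 E-RS and rescue-use means are counted back from the Week 48 visit, so they can lie up to 10 days from nominal Week 24 and up to 20 days from the patient's own Week 24 visit.

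*SAP*

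**What the plan says.** SAP 6.4 gives three rules for placing diary data into weeks.

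- **24-week subset, patients who stay in the study:** weeks are counted back from the Week 24 visit ("Week 24 = Actual study Day of Week 24 visit minus 7 days", up to that visit).
- **48-week subset, patients who stay in the study:** weeks are counted back from the Week 48 visit ("Week 24 = Actual study Day of Week 48 visit minus 175 days", up to 168 days before it). These patients also attend a Week 24 clinic visit (Protocol 1.3).
- **Patients who leave the study early, either subset:** fixed study days. Week 24 is after Day 162 up to Day 169.

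The first two rules apply "For patients who completed the study or who discontinue study medication but continue in the study". On scope, SAP 6.4 states that "rescue medication data, E-RS/EXACT-PRO, e-diary data windowing conventions will be up to Week 24", while exacerbations use the weeks to Week 48. On tolerance: "Each visit (except for Day 1 visit) will have a ± 10 days window".

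SAP 16.2.1.2.1 and 16.2.1.3 take the weekly E-RS and rescue-use means from these windows and set a mean to missing if fewer than 4 days have data. SAP 16.2 analyses both at Weeks 6, 12 and 24. In SAP 7.4 the third test is the change "to the mean weekly value at Week 24 in COPD symptoms, as measured by daily diary". Rescue use is not in that list.

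**The concern.** A Week 24 endpoint should be fixed by what happens up to Week 24. Here, two 48-week patients with the same Week 24 visit date and the same diary can get different Week 24 values because one attends Week 48 early and the other late. If one of them leaves the study after Week 24, the anchor changes again, to fixed days. The protocol describes the two subsets as identical in their assessments over the first 24 weeks, but this derivation treats them differently.

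The endpoint matters. If E-RS fails, the formal tests of SGRQ total score, morning trough FEV₁, FEV₁ AUC0-4h and SGRQ responders do not follow. The same windows supply E-RS and rescue use at Weeks 6 and 12 and the E-RS responder variable. In addition, all available weekly means enter the first imputation step for weekly endpoints (SAP 16.2.2.1).

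**Working it through.** **Inputs.** Window rules and ±10-day tolerance: SAP 6.4. Nominal Week 24 ends on Day 169 and nominal Week 48 on Day 337: fixed-day lists in SAP 6.4. Subset sizes and ratios: Protocol 1.1. Each week is read as starting the day after the previous week ends, which gives 7 days. V24 and V48 are the study days of the two visits.

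**1. Reproduce the nominal week.** With V48 = 337: 337 − 175 = 162 and 337 − 168 = 169, so Days 163-169. This matches the fixed-day rule exactly. The 24-week rule with V24 = 169 gives the same days.

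**2. Move the Week 48 visit.** The shift from nominal is s = V48 − 337. The overlap with nominal Week 24 is max(0, 7 − |s|) days.

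| V48 | Week 24 window | Overlap (days) |
|---|---|---|
| 327 | 153-159 | 0 |
| 330 | 156-162 | 0 |
| 334 | 160-166 | 4 |
| 337 | 163-169 | 7 |
| 340 | 166-172 | 4 |
| 344 | 170-176 | 0 |
| 347 | 173-179 | 0 |

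**3. Compare with the patient's own Week 24 visit.** The shift is (V48 − 168) − V24. At the extremes, V48 = 347 and V24 = 159 give 179 − 159 = 20 days.

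**4. How often.** The documents give no distribution of visit dates, so these are assumptions.

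- *Uniform over ±10 days, against nominal:* mean absolute shift 2 × (1 + … + 10)/21 = 110/21 = 5.2 days; no overlap in 8/21 = 38%.
- *Both visits uniform and independent, against own Week 24 visit:* a difference of d days arises in 21 − |d| of the 441 pairs. Mean absolute shift is 3,080/441 = 7.0 days; no overlap in 210/441 = 48%.
- *Visits kept within ±3 days:* maximum shift 3 days from nominal and 6 from the own visit; always some overlap.

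**5. Share of each arm under the rule, as randomised.** Ensifentrine: 400 × 3/4 = 300 of 500 (60%). Placebo: 400 × 1/4 = 100 of 300 (33%). The actual shares are lower, because patients who leave the study use fixed days.

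**6. Possible effect on the treatment difference.** No E-RS SD, effect or time course is given. For illustration, assume a drift of 0.05 to 0.2 points per week common to both arms, and a shift of 5 to 10 days in the same direction for every affected patient. The effect is (0.60 − 0.333) × drift × days/7. The smallest is 0.267 × 0.05 × 5/7 ≈ 0.01 points and the largest 0.267 × 0.2 × 10/7 ≈ 0.08 points. The E-RS responder threshold is 2 points (SAP 16.3.1.7).

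**7. Week 1.** With V48 = 327, Week 1 runs from 327 − 336 = −9 to 327 − 329 = −2, wholly in the run-in, and it reuses days that form the E-RS baseline. The 24-week subset has the same problem: V24 = 159 gives 159 − 168 = −9 to 159 − 161 = −2.

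**The case against.** Several points on the other side stand.

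- **The week is not always wrong.** A reader might infer that the endpoint is measured in the wrong week for every 48-week patient. It is not. The error equals the Week 48 visit's deviation from Day 337; it is partial up to 6 days, and a wholly different week arises only from 7 days.
- **Part of the 7-day, 48% figure is the Week 24 visit's own scatter.** Under the same uniform assumption, a window anchored on the Week 24 visit also lies 5.2 days from nominal on average. The fix aligns the diary week with the visit; it does not align it better with time since first dose.
- **Unequal membership is not bias.** A reader might infer from 60% against 33% that the treatment comparison is biased. That would need shifts that tend in one direction together with a time trend in E-RS, and the documents show neither. With symmetric visit scatter the mean shift is zero in each arm.
- **Rescue use is not gated**, and Week 1 is not itself an analysed time point. In the second imputation step only the weeks that match scheduled visits are used.
- **The text could be read differently.** The statement limiting diary windows to Week 24 could mean that the 24-week list serves everyone. The separate heading for the 48-week subset, with its own Weeks 1-24, supports the literal reading. If the other reading was intended, the SAP needs to say so.

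None of this justifies anchoring a Week 24 endpoint on a visit 24 weeks later, and the SAP offers no reason for it.

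**Conclusion.** The inconsistency is real and should be corrected before unblinding. For in-window visits, the 48-week subset's Week 24 mean may lie up to 10 days from nominal Week 24 and up to 20 days from the patient's own Week 24 visit. It coincides with nominal Week 24 only when the Week 48 visit falls on Day 337. Those limits follow from the SAP alone; the 38% and 48% rest on uniform visit dates (the 48% also on independence), which the documents do not support or exclude.

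The consequence is misalignment and noise in a gated endpoint. No reversed conclusion and no directional bias are shown, and the illustrative effect of 0.01 to 0.08 points is small.

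One uncertainty remains. SAP 16.2.1.2.1 says E-RS data are collected daily throughout the study, but the eDiary collection row in the Schedule of Activities is not legible in the text available. If diary entry stopped at the Week 24 visit, a window ending 4 or more days after it would have fewer than 4 diary days and the mean would be set to missing.

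**What to change.** For E-RS/EXACT-PRO and rescue use only, define Weeks 1-24 in both subsets by counting back from the patient's actual Week 24 visit. Where there is no such visit, use the SAP's existing fixed study days. In either subset, do not let Week 1 start before Day 1. This extends the SAP's own 24-week rule and brings the shift from the Week 24 visit to 0 days for everyone who attended it. Weeks 6 and 12 would then follow one rule in both subsets, though still counted from the Week 24 visit.

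Leave the weekly grid for COPD exacerbations to Week 48 unchanged. Splitting that grid at Week 25 would do harm: visits on Days 159 and 347 would leave Days 160-179 in no week, and visits on Days 179 and 327 would put Days 160-179 in two weeks. The diary-based drug-compliance intervals that run to Week 48 (SAP 15.1.1) can stay on the continuous grid for the same reason.

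The cost is a small SAP and programming change, with diary and exacerbation weeks defined separately. No new data are needed.
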